Justification: Controlling homeostatic plasticity can reduce subject variability^{2;3} and the knowledge gained can be used to optimize rTMS treatment. What is needed to move the field forward is a method for combining tDCS and rTMS and for measuring neuronal responses directly which we aim to establish in this study. The long term goal of our work is to optimize rTMS as a treatment for tinnitus. The project will examine the targeted effects of neuromodulation in normal subjects and in patients with tinnitus. The brain regions targeted for intervention include auditory areas in the temporal cortex (TC) that process sounds and functionally connected regions of the dorsolateral frontal cortex (DLFC) that mediate sensory habituation. Further, we aim to determine how neuromodulation suppresses sound perception.

Objectives: One overall objective of this pilot study proposal is to determine how different activation states of the TC and DLFC (their homeostatic plasticity) interact with different doses of rTMS (1 Hz and 10 Hz) to produce LTD and whether these physiological changes can affect tinnitus-like behavior in normal subjects. Transcranial direct current stimulation (tDCS) will be used to modulate the activation states of TC and DLFC prior to rTMS. The primary outcome measure is change in cortical excitability, which will be measured *directly* from TC and DLFC using TMS evoked EEG potentials (TEPs). A 128 channel EEG recording cap with embedded high density tDCS electrodes was specifically designed by our research team to interleave TMS/EEG recording with tDCS and rTMS delivery. A second objective, is to investigate how

Study Title: Regulating homeostatic plasticity and the physiological response to rTMS
PI: [name]
Institution: University of Arkansas for Medical Sciences
Support: Department of Neurobiology and Dev. Scs.

tDCS preactivation of the DLFC prior to 1 Hz rTMS of the TC modifies cortical excitability (TEPs) and perception of tinnitus in a patient sample.

Hypothesis: Our central hypothesis for this pilot study is that increased cortical activation will facilitate the induction of LTD by rTMS, both at the treatment site in TC and in a network site in the DLFC. In patients with tinnitus, it is hypothesized that LTD induction will correlate with change in tinnitus perception.

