Specific Aim 1: Determine in normal healthy subjects how increased activation of the TC modifies the induction of LTD by 1 Hz and 10 Hz rTMS. Analyses will examine difference scores between sham and active rTMS in the local mean field power (LMFP) of TEPs (Δ LMFP) recorded from TC and DLFC. Parallel groups of healthy subjects (n=5 each) will receive 1 and 10 Hz rTMS. Four contrasts are of interest – (1) sham vs active tDCS for 1 Hz rTMS, (2) sham vs active tDCS for 10 Hz rTMS, (3) 1 Hz vs 10 Hz rTMS for sham tDCS, and (4) 1 Hz vs 10 Hz rTMS for active tDCS. Our working hypothesis is that increased cortical activation will facilitate LTD following rTMS at both frequencies of stimulation, but the effect for 1Hz will be stronger for than for 10 Hz.

Specific Aim 2: Determine in normal healthy subjects how increased activation of the DLFC modifies LTD induced by 1 Hz and 10 Hz rTMS over the TC. New groups of subjects will be recruited. The design, analyses, and predictions are the same as for Aim 1. The difference is that circuits in the DLFC, a functionally connected network, are being preconditioned rather than TC. We predict that rTMS delivered to the TC will induce LTD in the DLFC after it has been preconditioned with tDCS.

Exploratory Aim. We will develop and test a behavioral model of sound perception in healthy participants who have normal hearing by placing them in a sound attenuated environment and measuring ratings of sounds played above threshold. We will examine how tDCS/rTMS modify these perceptions.

Specific Aim 3: Determine in patient with tinnitus how increased activation of the DLFC modifies LTD and tinnitus perception induced by 1 Hz rTMS over the TC. We will recruit ten subjects from a previous study of rTMS for tinnitus (109033) who agreed to be contacted for future research projects. We will examine change from baseline in TEPs (Δ LMFP) recorded from TC and DLFC and on ratings of tinnitus awareness, annoyance and loudness following three days of treatment (tDCS preconditioning of the DLFC followed by 1 Hz rTMS of the TC). Analyses will examine change from baseline for TEPs and tinnitus ratings. Change scores for tinnitus ratings will be compared to those for sham and active rTMS treatments from a previous study (109033).

Aims 1 & 2 Design: A randomized, blinded, sham controlled, mixed effects model with assignment to two treatment arms (1 or 10 Hz rTMS) and three experimental

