Study Title: Regulating homeostatic plasticity and the physiological response to rTMS
PI: [name]
Institution: University of Arkansas for Medical Sciences
Support: Department of Neurobiology and Dev. Scs.

conditions within each arm (Table 1). Subjects will be sequentially assigned to one of two parallel groups (1 Hz or 10 Hz rTMS).

Study endpoints: The primary outcome measure is the local mean field potential calculated for electrodes over the temporal and dorsolateral frontal cortex that are measured at baseline and after sham and active treatment conditions. An exploratory outcome measure is ratings of auditory stimuli detected by participants before and after each of the three experimental conditions.

Statistical Plan or Data Analysis: Aims 1 & 2 examine the effect of treatment dose on one primary outcome measure – a difference score between sham and active rTMS in the LMFP of TEPs (Δ LMFP) recorded from TC and DLFC. The analysis plan is the same for both aims. Hierarchical Linear Models (HLMs) will be used due to the nested structure of the design. HLMs will fit the complex covariance structure of the dosing schedule – sham and active tDCS nested within rTMS treatment frequency (1 Hz and 10 Hz).

Trial design, endpoints and analysis for Aim 3. The design is an open label, feasibility study – a pre-post examination of change in the LMFP of TEPs (Δ LMFP) recorded from TC and DLFC and in the ratings of tinnitus awareness, loudness and annoyance after four days of treatment. Aim 3 is conceptually similar to Aims 1 and 2 in using tDCS preconditioning of rTMS and in using EEG to evaluate change; however, treatment length and the timing and methods of assessing tinnitus were adopted from a previous study so that the data would be comparable.

What are the test articles TMS and tDCS?

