Up to ten subjects with tinnitus who participated in a previous rTMS study (i.e., 109033) and who agreed to be contacted for future studies will be invited to participate. The design of Aim 3 is an, open-label, feasibility study with pre and post assessments. All subject visits will be to the TMS laboratory and the Brain Imaging Research Center (BIRC) of the Psychiatric Research Institute. There will be a total of four study visits to the TMS laboratory, with one visit including a walk to the BIRC for the MRI scan, and three follow-up phone calls, emails or text messages used to obtain tinnitus ratings. The time required for each visit ranges from 1 hour when TMS/EEG is not measured to 3.5 hours when TMS/EEG is measured. During the first visit, subjects will complete the informed consent process and reestablish that they meet inclusion and do not meet the exclusion criteria. They will then complete a baseline TMS/EEG recording and make analogue ratings of tinnitus awareness, loudness and annoyance. An MRI image of the brain may be acquired as part of the first or second visit. During visits 2-4, subjects will be treated with tDCS over the DLFC (2 mA for 20 minutes) prior to receiving rTMS over the TC (1800 pulses delivered at 1 Hz and 110% of motor threshold). Following the treatment during visit four, subjects will have their second TMS/EEG recording. The study endpoints are the same as those in Aims 1 and 2 except that actual ratings of tinnitus are used in place of the procedure for measuring tinnitus like perception in healthy subjects.

Study Population

Aims 1 & 2

Study subjects will be recruited via advertisement. Twenty (20) healthy subjects between the ages of 19-65 years will be recruited. Screening measures include the Transcranial Magnetic Stimulation Adult Safety Screen (TASS).³⁷ A request for medical records either from UAMS or an external service provider may be necessary to ensure that subjects do not meet exclusion criteria.

Inclusion Criteria

- 1) complete the informed consent process
- 2) men and women, age: 19–65 years (a range reflective of our tinnitus samples, (e.g., CLARA IRB# 109639 *PET-CT to target and validate TMS as treatment for Tinnitus*)
- 3) negative pregnancy test (female subjects of childbearing age must take a pregnancy test).

Study Title: Regulating homeostatic plasticity and the physiological response to rTMS
PI: [name]
Institution: University of Arkansas for Medical Sciences

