Methods for TMS targeting. A template MRI scan will be uploaded into the Brainsight frameless stereotaxy system (Rouge Research, Montréal, Québec, Canada) and used to track stimulation delivery for all subjects. Brainsight uses 3D infrared tracking position sensors to reference the MRI to anatomical landmarks on the subject's head and to the TMS coil. Digitized markers can be placed on the MRI in Brainsight to ensure that the TMS coil is placed in the same locations from session to session. Brainsight will be used to target rTMS over the caudal two-thirds of the superior temporal gyrus (BA 22 in TC). During TEP recording, Brainsight will be used to target the TMS coil over BA 22 in the TC and to position the TMS coil over the convexity of the superior frontal gyrus where TEPs from the DLFC will be obtained. All stimulation sites will be marked in the Brainsight Stereotaxic system (RougeResearch) to ensure precise session to session targeting.

Methods for active and sham rTMS and study blinding. The MT will be established at the

Figure 5. Electrode location mock-up.

Study Title: Regulating homeostatic plasticity and the physiological response to rTMS
PI: [name]
Institution: University of Arkansas for Medical Sciences
Support: Department of Neurobiology and Dev. Scs.

beginning of each test session. A technician will set up equipment for each test session while the subject is being prepped for EEG recording, to keep them blind to condition. To check integrity of the blind, subjects will be asked to guess whether they received active or placebo stimulation at the end of each treatment session. Subjects are not providing subjective responses to intervention, which minimizes the possibility of experimenter bias. Persons who process EEG data for analysis and the biostatistician will be kept blind to condition using session codes. These procedures were used successfully in previous studies.⁴⁵

Aim 3.

The methods for tDCS preconditioning in Aim 3 is identical to that described for Aims 1 and 2 except that the high density stimulating electrodes will be placed in a cap specifically designed by the manufacture rather than the 128 channel EEG recording cap (as in Aims 1 & 2). Additionally, only active tDCS will be delivered.

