Patients will be asked to have a structural MRI scan. For safety reasons and prior to the MRI scan, subjects may have a training session in the MRI simulator to help habituate and train them to the MRI environment. Per the MRI Policies and Procedures, the decision of who will be acclimated in the MRI Simulator will be made by the Research Coordinators and PI on a case-by-case basis. The PI for the study will have final say in this decision. Before the MRI scan, participants will be given an explanation of the study's procedures and screened with the MRI Safety Form for metal objects and claustrophobia. Participants will also be screened with the SAFESCAN® ferromagnetic detector according to MRI Policy and Procedures. The participant will then lie supine in the scanner. Participants will wear noise-cancelling headphones for communication and view visual stimuli through a mirror attached to the imaging head coil. Participants will undergo an anatomic scan.

The method for rTMS stimulation of the TC and for establishing the motor threshold is also identical to that described for Aims 1 and 2 except that 1800 pulses are delivered rather than 900 pulses and only active stimulation at 1 Hz will be used.

tDCS preconditioning of the DLFC will be delivered immediately prior to rTMS stimulation of the TC for three days within a one week period. rTMS will be targeted over the TC as described for Aims 1 and 2. The same safety measures will be performed before and after stimulation on each day of treatment. Additionally, analogue ratings (using a 0-100 scale) of tinnitus awareness, annoyance and loudness will be obtained at baseline and before and after each treatment session. The same ratings will also be obtained via phone, text or email on day 2, day 9 and day 16 following the last treatment. The necessary length of treatment and the timing and methods used to assess tinnitus were adopted from a previous study (109033) to ensure that the data

Study Title: Regulating homeostatic plasticity and the physiological response to rTMS
PI: [name]
Institution: University of Arkansas for Medical Sciences
Support: Department of Neurobiology and Dev. Scs.

are comparable between studies.

To assess changes in cortical excitability, EEG without and with TMS will be recorded during the baseline visit and following treatment on visit four. The primary outcome measure for TMS evoked EEG and the equipment used to assess TMS evoked EEG are described next.

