Aim 3 is being conducted as an open label feasibility study. The data may be used to derive power estimates for future studies. Subjects in this study will have completed sham and active 1 Hz rTMS treatments for tinnitus in a previous study (109033). The length of treatment, time of assessments and ratings of tinnitus used for Aim 3 are based on the previous study (109033). Therefore, we will compare change scores from baseline derived for the ratings of tinnitus in Aim 3 to changes scores from baseline derived from the sham and active 1Hz rTMS treatments in study 109033. HLMs will be used to compare mean scores for each treatment condition to provide an estimate of effect size which can be used for power calculations.

To examine change in cortical excitability following treatment, the LMFP of TEPs derived for regioins of the DLFC and temporal cortex will be compared before and after treatment using paired t-tests.

Ethical Considerations

This study will be conducted in accordance with all applicable government regulations and University of Arkansas for Medical Sciences research policies and procedures. This protocol and any amendments will be submitted and approved by the UAMS Institutional Review Board (IRB) to conduct the study.

The formal consent of each subject, using the IRB-approved consent form, will be obtained before that subject is submitted to any study procedure. All subjects for this study will be provided a consent form describing this study and providing sufficient information in language suitable for subjects to make an informed decision about their participation in this study. The person obtaining consent will thoroughly explain each element of the document and outline the risks and benefits, alternate treatment(s), and

Study Title: Regulating homeostatic plasticity and the physiological response to rTMS
PI: [name]
Institution: University of Arkansas for Medical Sciences
Support: Department of Neurobiology and Dev. Scs.

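### Aim 3 cannot show how DLFC preactivation modifies LTD, because no TEP is recorded after rTMS without active tDCS; the tinnitus-rating half has a comparator, but only a weak historical one

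*Combined protocol and SAP*

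**What the plan says.** **The question.** Specific Aim 3 in the Protocol Summary is to "Determine in patient with tinnitus how increased activation of the DLFC modifies LTD and tinnitus perception induced by 1 Hz rTMS over the TC". The second objective, under Objectives, asks how "tDCS preactivation of the DLFC prior to 1 Hz rTMS of the TC modifies cortical excitability (TEPs) and perception of tinnitus in a patient sample".

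**The design.** The Protocol Summary describes it plainly: "The design is an open label, feasibility study – a pre-post examination of change in the LMFP of TEPs". The Aim 3 part of Study Design says: "During visits 2-4, subjects will be treated with tDCS over the DLFC (2 mA for 20 minutes) prior to receiving rTMS over the TC". The Aim 3 part of Apparatus, Materials, and Procedures adds, on tDCS, "Additionally, only active tDCS will be delivered", and, on rTMS, that "1800 pulses are delivered rather than 900 pulses and only active stimulation at 1 Hz will be used".

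**TEP recording and analysis.** The same Aim 3 procedures state: "To assess changes in cortical excitability, EEG without and with TMS will be recorded during the baseline visit and following treatment on visit four". At the end of Power Estimates, the LMFP values for the two regions "will be compared before and after treatment using paired t-tests". No other TEP analysis is given for Aim 3.

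**The outside comparator.** Specific Aim 3 and Power Estimates plan to compare changes in tinnitus ratings with the changes under sham and active 1 Hz rTMS in study 109033, using hierarchical linear models. Power Estimates says that the Aim 3 patients completed both of those treatments there. The comparison covers ratings only. Nothing in the protocol says that TEPs from 109033 exist or will be used.

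**The concern.** To say how one treatment modifies the effect of another, the second treatment's effect must be seen with and without the first. The protocol uses the verb this way itself. Aims 1 and 2 are also worded as how activation modifies LTD, and they answer with contrasts of sham against active tDCS within each rTMS frequency. Aim 3 keeps the verb and drops the contrast for TEPs.

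What is at stake is the conclusion that may be drawn from a before-after difference in LMFP. The section on what is unique about the proposal, just after describing the DLFC preconditioning added in Aim 3, says that finding LTD in the DLFC after TC stimulation would confirm the expected interaction between the two circuits. Applied to Aim 3, a fall in DLFC LMFP between visit 1 and visit 4 would meet that description. Yet it could come from tDCS acting on the DLFC directly, from rTMS alone, from the two together, or from drift between recordings.

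**Working it through.** The protocol gives no power, sample-size or alpha figure for Aim 3, so there is nothing to reproduce. The check is whether the quantity in the aim can be estimated from the planned TEP recordings.

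**Step 1: what is recorded.**

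| TEP recording or condition | Aims 1 and 2 (Table 1) | Aim 3 |
|---|---|---|
| Before any stimulation | yes | yes, visit 1 |
| Between tDCS and rTMS | yes | no |
| After active rTMS with sham tDCS | yes | no |
| After sham rTMS with sham tDCS | yes | no |
| After active rTMS with active tDCS | yes | yes, visit 4 |

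**Step 2: the model.** Let b be mean baseline LMFP, r the change that 1 Hz rTMS would produce without tDCS, and m the further change due to tDCS preactivation. Aim 3's LTD question is about m. Leave drift out for now, which favours the plan.

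- Baseline mean = b, design row (1, 0, 0).
- Visit 4 mean = b + r + m, design row (1, 1, 1).

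Two rows give rank 2 for three parameters. The paired difference estimates (b + r + m) − b = r + m, and only that sum. More patients narrow its confidence interval but do not separate r from m.

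If m is split into a direct tDCS effect and a tDCS-by-rTMS interaction, and retest drift is added, there are five parameters and still rank 2.

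**Step 3: what would make m estimable.** A TEP change under 1 Hz rTMS without active tDCS adds the row (1, 1, 0). The rank becomes 3, and m is the difference between the two changes.

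**Step 4: what the planned test responds to.** This is an illustration. Assumptions: n = 10 (the maximum), two-sided alpha 0.05, no drift, and d = (r + m) divided by the SD of the paired differences. Power comes from the noncentral t distribution with n − 1 = 9 degrees of freedom and noncentrality d√n. Set m = 0, so tDCS does nothing:

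| rTMS-alone change, d | d√10 | P(significant paired t-test) |
|---|---|---|
| 0 | 0 | 0.05 |
| 0.5 | 1.58 | 0.29 |
| 1.0 | 3.16 | 0.80 |
| 1.5 | 4.74 | 0.99 |

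With no modification at all, the chance of a significant result runs from 0.05 to 0.99 depending only on the rTMS effect. The reverse also holds: if r and m were equal and opposite, for example +0.5 and −0.5, then d = 0 and the test would be significant with probability 0.05 although modification is present. The smallest total change detectable with 80% power at n = 10 is d of about 1.0, and that is a statement about r + m.

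**The case against.** **Aim 3 is declared a feasibility study.** The protocol says so more than once, describes the analysis as change from baseline, and says the data may serve future power calculations. It sets no significance level or success criterion for this aim. All of that stands, and it limits the consequence. It does not change an aim and an objective that promise to determine a modification. A reader might infer that a significant paired test is certain to be reported as the answer to Aim 3. The documents do not say that. The nearest text is the sentence about confirming the circuit interaction, which concerns TC and DLFC interaction rather than preactivation as such.

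**Study 109033 is a comparator.** For ratings it is, and a reasonable one for a pilot: the same people, with treatment length, assessment times and rating methods taken from that study. For TEPs it offers nothing.

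**Aim 2 tests DLFC preactivation under control.** It does, so the protocol does not depend on Aim 3 alone for that contrast. But its 1 Hz group is 5 healthy subjects given 900 pulses per session, against three sessions of 1800 pulses (3 × 1800 = 5400) in patients, and no analysis across the aims is planned. It does not fill the gap in patients.

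**The Aim 3 hypothesis needs no tDCS-free condition.** It concerns correlation between LTD induction and change in tinnitus perception. That is correct, and the point here does not touch it.

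**Preferring an interval to a p-value is reporting style.** Agreed. A confidence interval on a confounded change is just as confounded. What matters is the statement of what the change represents.

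**Conclusion.** The point holds for the LTD/TEP half of Aim 3 and of the second objective. No patient, of up to 10, contributes a TEP after 1 Hz rTMS without active tDCS. The contribution of preactivation to LMFP change is therefore not identifiable at any sample size. This rests on the protocol's own schedule and needs no assumed effect size; the probabilities above are illustrative and depend on the stated assumptions.

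A reader might infer that Aim 3 as a whole cannot be answered, or that no effect of preactivation is estimated anywhere in it. The documents do not support that. The tinnitus-rating half has a planned comparison with the same subjects' rating changes under sham and active 1 Hz rTMS without tDCS in 109033. That comparison is historical and non-randomised, and the new ratings are given open label, so period and expectation effects are mixed with any effect of tDCS. Its answer is weak, not absent.

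**What to change.** Make four wording changes:

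1. In Specific Aim 3 and the second objective, restate the TEP part as estimating, with a 95% CI, the change in LMFP in TC and in DLFC from before to after combined DLFC tDCS and TC rTMS. The paired t-test may stay as the accompanying test.
2. State there, and beside the paired analysis in Power Estimates, that the effect of preactivation on TEPs is not estimated in Aim 3.
3. In the section on what is unique about the proposal, limit the statement about confirming the circuit interaction in the same way where it is applied to Aim 3.
4. Keep the tinnitus-rating endpoint and the hierarchical-model comparison with 109033 unchanged, and label that comparison historical and non-randomised, with Aim 3 ratings given open label.

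The cost is a narrower claim. No subject, visit, recording or analysis is added or removed. Keeping the present wording for TEPs would instead require a TEP change under 1 Hz rTMS without active tDCS in these patients, which is a change of design.

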Study Design, Population, Apparatus and Investigational Plan

Aims 1 & 2.

Design: This is prospective, experimental design includes a block randomized, blinded, sham controlled, mixed effects model with sequential assignment to two treatment arms (1 or 10 Hz rTMS) and random assignment to three experimental conditions within each arm (Table 1).

Randomization: Subjects will be assigned sequentially to one of two parallel groups (1 Hz or 10 Hz rTMS: Table 1.5). Next, they will complete three experimental test sessions (Table 1). The order of test sessions is randomized. A minimum two week washout period will follow each session to minimize session to session carry forward effects.¹⁵ Washout can exceed two weeks.

[figure not shown]

Figure 1.5. Subject flow.

Study visits: Study visits will be to the transcranial magnetic stimulation laboratory, room 654-2, located on the 6th floor of the Biomedical II research building on the UAMS

Study Title: Regulating homeostatic plasticity and the physiological response to rTMS
 PI: [name]
 Institution: University of Arkansas for Medical Sciences
 Support: Department of Neurobiology and Dev. Scs.

campus. In total, there will be 4 study visits - 1 consent/screening visit and 3 laboratory visits per subject. The 3 laboratory study visits will be separated in time by a minimum of two weeks. The time required to complete a study visit ranges from 1 hour, when TMS/EEG is not collected, to 3.5 hours, when TMS/EEG is collected. TMS/EEG is recorded immediately before and after tDCS preconditioning, immediately following rTMS and after a 20-30-minute delay to examine the acute and lasting effects.

Subject flow: Twenty healthy subjects who meet the entry criteria and pass safety screening for tDCS and TMS will be enrolled (Figure 1.5). Ten subjects will be tested in each aim, with two parallel groups of 5 subjects receiving either 1 or 10 Hz rTMS. Two randomization lists of 10, each balanced between tDCS over TC and tDCS over DLFC, were generated based

on uniformly distributed random number generation in SAS v9.4. The first 10 recruited subjects will receive 1Hz rTMS treatment while the second 10 will receive

Experimental conditions & TMS/EEG assessments.								
Condition†	TMS/EEG	tDCS	TMS/EEG	rTMS	TMS/EEG	30 min delay	TMS/EEG	
1		sham		sham				
2		sham		active				
3		active		active				
Time (mins)	0	20	40	60	80	100	130	

Table 1. † The order of conditions is randomized. A 2 week washout separates each condition.

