Data collection will be accomplished via case report forms and electronic recording via the devices used in this study. The Principal Investigator will carefully monitor study procedures to protect the safety of research subjects, the quality of the data and the integrity of the study. Participant's data will be de-identified using codes, personal identifiers will be kept separate from study data, and data will be locked in file cabinets or drawers in the TMS laboratory and in the PI's office, if hardcopy, or on a password-protected UAMS server, both located behind locked doors in a restricted access area of the UAMS campus. Only authorized individuals will have access to the code and information that identifies the subjects in this study. Following informed consent to participate, patient's hospital and outpatient records may be reviewed to identify appropriate candidates for the study. Any data obtained as part of the patient's clinical care may be reviewed to determine whether the subject meets inclusion and does not meet exclusion criteria.

Data Analysis

Analyses and Power calculations.

Aims 1 & 2 examine the effect of treatment dose on one primary outcome measure – a difference score between sham and active rTMS in the LMFP of TEPs (Δ LMFP) recorded from TC and DLFC. The analysis plan is the same for both aims. Hierarchical Linear Models (HLMs) will be used due to the nested structure of the design. HLMs will fit the complex covariance structure of the dosing schedule – sham and active tDCS nested within rTMS treatment frequency (1 Hz and 10 Hz). Four primary responses will be estimated, namely Δ LMFP for the sham vs active tDCS and the 1 Hz vs 10 Hz rTMS conditions. From these four responses, four contrasts of interest will be estimated: (1) sham vs active tDCS for 1 Hz rTMS, (2) sham vs active tDCS for 10 Hz rTMS, (3) 1 Hz vs 10 Hz rTMS for sham tDCS, and (4) 1 Hz vs 10 Hz rTMS for active tDCS. An additional 6 contrasts will be used to examine differences in the means for the rTMS post 1 (acute) and post 2 (lasting) time periods. The HLM methodology will estimate the means and standard errors for all these contrasts of interest with a Bonferroni comparison procedure to adjust for the multiple contrasts.

Power Estimates

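### rTMS frequency follows enrolment order, so the 1 Hz versus 10 Hz contrasts are confounded with any early/late change in response to rTMS, and the plan sets no limit on their interpretation

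*Combined protocol and SAP*

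**What the plan says.** The Design paragraph for Aims 1 & 2 (Study Design, Population, Apparatus and Investigational Plan) describes "sequential assignment to two treatment arms (1 or 10 Hz rTMS) and random assignment to three experimental conditions within each arm (Table 1"). The Protocol Summary agrees: "Subjects will be sequentially assigned to one of two parallel groups (1 Hz or 10 Hz rTMS"). Subject flow gives the rule itself: "The first 10 recruited subjects will receive 1Hz rTMS treatment while the second 10 will receive" 10 Hz.

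Two things are randomised. One is the tDCS site: "Two randomization lists of 10, each balanced between tDCS over TC and tDCS over DLFC, were generated based" on random numbers. The other is the order of the three conditions within each subject. Each aim has 5 subjects per frequency.

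The frequency comparison is then treated as a test:

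- Specific Aim 1 predicts facilitation of LTD at both frequencies, "but the effect for 1Hz will be stronger for than for 10 Hz". Aim 2 takes over the same predictions.
- Data Analysis lists, among the four contrasts of interest, "3) 1 Hz vs 10 Hz rTMS for sham tDCS, and (4) 1 Hz vs 10 Hz rTMS for active tDCS".
- It adds time-period contrasts ("An additional 6 contrasts will be used to examine differences in the means") and one adjustment for all of them: "The HLM methodology will estimate the means and standard errors for all these contrasts of interest with a Bonferroni comparison procedure".
- Power Estimates gives contrast 4 its own power (94% acutely, 8% at 30 minutes) and closes by judging the sample sizes adequate for Aims 1 and 2.

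The model description names no term for enrolment period, and no section qualifies the conclusions about frequency.

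**The concern.** The groups compared in contrasts 3 and 4 are the first ten and the last ten recruits. Anything that alters the response to active rTMS between them, such as operator experience with a newly designed cap or a different mix of volunteers answering advertisements, enters those contrasts in full. It could appear as a frequency effect or hide one. A Bonferroni correction lowers the rejection rate but leaves the bias in the estimate. At stake is half of the set of four main contrasts, together with the comparative part of the working hypothesis.

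**Working it through.** **1. The plan's own figure.** Power Estimates uses a two-sample t-test with n = 5 per group. Alpha and sidedness are not stated; I assume two-sided 0.05.

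- Effect size from the stated means and SDs: (0.98 − 0.64)/√((0.08² + 0.16²)/2) = 0.34/0.1265 = 2.69 (stated 2.68).
- Noncentral t, 8 df: d = 2.68 gives 95.8% (stated 94%); d = 0.39 gives 8.5% (stated 8%).

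Both reproduce closely. They assume exchangeable groups, so they say nothing about this bias.

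**2. What cancels and what does not.** For one subject, let a be the LMFP level, R the change produced by active rTMS after sham tDCS, and T the further change when tDCS is active. The sessions are then a (sham/sham), a + R (sham/active) and a + R + T (active/active). Up to sign, ΔLMFP is R under sham tDCS and R + T under active tDCS. Suppose late recruits differ from early ones by s in a, r in R and t in T.

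| Comparison | Estimates | Early/late change that enters |
|---|---|---|
| Contrasts 1, 2 | T within one frequency group | none; both sessions come from the same subject |
| Contrast 3 | frequency effect on R | r |
| Contrast 4 | frequency effect on R + T | r + t |
| Stronger at 1 Hz (contrast 1 versus 2) | frequency effect on T | t only |

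The level shift s drops out everywhere.

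**3. Can a model separate them?** With intercept, frequency, site and their interaction, the 20-subject design matrix has rank 4. Adding an enrolment-half column gives 5 columns and still rank 4, so a step between halves cannot be estimated separately. A linear trend can be, but poorly. Positions 1–20 have SD √(399/12) = 5.766 and the halves differ by 10 positions, so the correlation with frequency is 10 × 0.5/5.766 = 0.867. The variance inflation is 1/(1 − 0.867²) = 4.03, which doubles the standard error (√4.03 = 2.01). Within one aim the 95% interval half-width is 2.306 × √(2/5) = 1.46 SD without the trend. With it the half-width is about 3.11 SD (7 df, median standard-error inflation 2.08 over simulated lists).

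**4. False-positive rate with no frequency effect.** The shift δ, in SDs of ΔLMFP, is an assumption. Noncentrality is δ√(5/2) = 1.581δ, with 8 df, two-sided.

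| δ | alpha 0.05 | 0.05/4 = 0.0125 | 0.05/10 = 0.005 |
|---|---|---|---|
| 0.3 | 7.1% | 2.0% | 0.8% |
| 0.5 | 10.8% | 3.3% | 1.5% |
| 1.0 | 28.6% | 11.4% | 5.8% |

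Dividing by ten (4 + 6 contrasts) is the natural reading of Data Analysis. Coverage of an unadjusted 95% interval is 100% minus the first column: 92.9%, 89.2% and 71.4%.

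**5. One blocked list instead.** Take five blocks of four, each holding every frequency-by-site cell once. Expected bias is zero.

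- *Step at subject 10:* only the third block (positions 9–12) straddles it, so within one aim at most 1 of 5 pairs is split: 1/5 = 20% of the step.
- *Linear drift:* the extreme list puts 1 Hz at positions 1, 5, 9, 13, 17 (mean 9) and 10 Hz at 4, 8, 12, 16, 20 (mean 12). The difference is 3, against 10 between halves: 30% of the gap.

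**The case against.** **Disclosure.** The protocol sets sequential assignment of frequency against random assignment of conditions. A reader might infer that it presents frequency as randomised; the documents do not support that. Only the consequence for interpretation is missing.

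**The hypothesis.** A reader might infer that the prediction of a stronger effect at 1 Hz is confounded in the same way as contrasts 3 and 4. It is not. It compares contrast 1 with contrast 2, so a change in rTMS response common to the sham- and active-tDCS sessions cancels as well. Only an early/late change in the tDCS effect remains, and the rates in the table were not derived for it.

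**Calendar time.** Each subject has three sessions at least two weeks apart, so late 1 Hz and early 10 Hz sessions may overlap in date. A change tied to session date would then be only partly confounded. The accrual period is not given, so this is possible but not established. A change in who is recruited is not eased by it.

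**Size.** No passage supports a particular shift. On the ten-contrast reading, 0.3 and 0.5 SD give only 0.8% and 1.5%. Motor threshold set each session and neuronavigation may also reduce drift. It is tempting to say that a 0.39 SD shift would cancel or double the plan's 30-minute effect. That effect is in SDs of motor-cortex MEP amplitude, with 5 Hz standing in for 10 Hz, whereas the shifts are in SDs of ΔLMFP, for which the plan says no data exist. The comparison is illustrative only.

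**Pilot status.** This is a 20-subject pilot, meant partly to supply data for power calculations, and its closing sentence on power concerns sample size rather than causation. That lowers the stakes. It does not supply the missing limit, because the plan still tests the contrasts.

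**Conclusion.** The point stands for contrasts 3 and 4: an early/late change in the response to rTMS cannot be told apart from a frequency effect, and the plan does not say so. For the hypothesis of a stronger effect at 1 Hz it stands only in the narrower form, as confounding with an early/late change in the tDCS effect. Contrasts 1 and 2 are sound on this score.

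The size is unknown. Under assumed shifts up to 1.0 SD of ΔLMFP the false-positive rate at 0.05/10 reaches 5.8%, about 11 times the nominal 0.5%; at 0.5 SD it is about three times nominal. These rates rest on normal data, equal variances and a t-test with 5 subjects per group as a stand-in for the hierarchical model. The bias in the estimates does not depend on those assumptions. This should be fixed, because the remedy needs no extra subjects and changes what the trial can claim about frequency.

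**What to change.** **If enrolment has not started:** replace the two sequential lists with one concealed list of 20 in five permuted blocks of four, each block holding each frequency-by-site cell once. The cost is a new list and an amendment. It also places 10 Hz sessions among the first subjects. The Seizures paragraph under Risks Associated with TMS ties reported seizures mainly to high frequencies, and the protocol gives no reason for its order. If the sponsor has a reason for running 1 Hz first, it should record it and keep the order.

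**If enrolment has started or the order stays:** state in Specific Aims 1 and 2, in Data Analysis and in all reports that the frequency comparison is non-randomised and confounded with enrolment period. Report contrasts 3 and 4 and the frequency hypothesis as estimates with confidence intervals, without a causal claim about frequency. This costs only text. Since Subject flow describes the lists as already generated, it may be the only option left. Adjusting for enrolment order is not a substitute, given the doubled standard error and the need to assume the form of the trend.
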